8.2 Discontinuation of Individual Subject(s) From Study

All subjects who discontinue study dosing will remain in the study and must continue to be followed for protocol-specific follow-up procedures as outlined in Schedule of Assessments [Table 1]. The only exception to this is when the subject specifically withdraws consent for any further contact with him/her or persons previously authorized by the subject to provide this information.

8.2.1 Lost to Follow-up

Every reasonable effort is to be made to contact any subject lost to follow-up during the course of the study to complete study-related assessments and record outstanding data.

8.3 Discontinuation of the Study Site

If an investigator intends to discontinue participation in the study, the investigator must immediately inform the sponsor.

8.4 Discontinuation of the Study

The sponsor may terminate this study prematurely, either in its entirety or at any study site, for reasonable cause provided that written notice is submitted in advance of the intended termination. Advance notice is not required if the study is stopped due to safety concerns. If the sponsor terminates the study for safety reasons, the sponsor will immediately notify the investigator and subsequently provide written instructions for study termination.

9 STATISTICAL METHODOLOGY

In general, all data will be summarized with descriptive statistics for continuous endpoints, and frequency and percentage for categorical endpoints, unless otherwise specified. Percentages by categories will be based on the number of subjects with no missing data (i.e., will add up to 100%).

Baseline will be defined as the last nonmissing observation prior to first administration of IP, unless otherwise specified.

9.1 Sample Size

A total of 24 subjects (12 subjects per dose group) will be enrolled. Subjects who discontinue early from the study may be replaced at the discretion of the sponsor.

Based on data from Study 178-CL-091, a Chinese phase 1 study, the intrasubject coefficient of variation (CV) for pharmacokinetic parameters AUC_{inf} , AUC_{last} and C_{max} of the 50 mg mirabegron dose are estimated to be between 33% and 60%. Assuming the underlying variability is similar to 60% and an observed ratio between fasted and fed conditions of 100%, the 90% CI will lie within (60, 167) with > 80% probability.

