All medicinal products other than the IP(s), including prescribed or nonprescribed drugs (including vitamins, natural and herbal remedies, e.g., St. John's Wort and traditional Chinese medicine), used from first IP administration until the ESV (including washout between periods) will be considered concomitant medication.

Subjects will only be allowed to use the following concomitant medication, if needed, from first IP administration until the ESV (including washout between periods):

- Paracetamol (up to 2 g/day)
- Topical dermatological products, including corticosteroid products
- Hormonal contraceptives
- HRT

If a subject's health condition necessitates the use of any medication other than the permitted medications during the study, the investigator and medical monitor, or designee(s), will discuss the case and determine if the subject should be withdrawn from the study and/or excluded from analysis sets, depending on if, and how, the medication(s) used influence(s) the study outcome. The nonpermitted concomitant medication will be recorded as a protocol deviation.

All concomitant treatment (medication and nonmedication therapy) will be documented.

Duration of Dosing:

Two single periods separated by a washout of at least 10 days between IP administrations in each period

Dosing Discontinuation Criteria:

A subject must discontinue study dosing for any of the following reasons:

- Subject requests to stop dosing
- Any clinical adverse event (AE), laboratory abnormality or intercurrent illness, in the opinion of the investigator, indicates continued dosing is not in the best interest of the subject
- Hepatic function parameters: ALT or AST $> 3 \times$ ULN and/or TBL $> 2 \times$ ULN
- Cardiac repolarization dysfunction: QTcF > 500 msec and/or if QTcF change from baseline > 60 msec at repeat measurements

Statistical Methods:

Sample Size Justification:

A total of 24 subjects (12 subjects per dose group) will be enrolled. Subjects who discontinue early from the study may be replaced at the discretion of the sponsor.

Based on data from Study 178-CL-091, a Chinese phase 1 study, the intrasubject coefficient of variation (CV) for pharmacokinetic parameters AUC_{inf} , AUC_{last} and C_{max} of the 50 mg mirabegron dose are estimated to be between 33% and 60%. Assuming the underlying variability is similar to 60% and an observed ratio between fasted and fed conditions of 100%, the 90% CI will lie within (60, 167) with $> 80\%$ probability.

Efficacy:

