The long-term effect of mirabegron was established by a 1-year study, Study 178-CL-049. Improvement in incontinence episodes, micturitions and mean volume voided per micturition was observed for mirabegron 50 and 100 mg once daily; results were similar to tolterodine. Improvement was also established in subjective endpoints as well as responder analyses indicating that the patients had clinically meaningful benefit from treatment.

Mirabegron at the proposed therapeutic dose is well-tolerated in the OAB population studied, inclusive of patients with multiple comorbidities and concomitant medications. The data from the clinical program are generalizable to the population of patients intended for the use of mirabegron in the treatment of OAB.

Adverse events (AEs) of interest have been thoroughly evaluated, generally do not represent product-related safety concerns, and where appropriate, can be addressed in labeling and other routine pharmacovigilance.

Preclinical and clinical safety data, including AEs of interest, support the safety of mirabegron under labeled condition in the treatment of patients with OAB.

The effect of food on the pharmacokinetics of mirabegron has been evaluated in healthy subjects in the US and Japan [Studies 178-CL-041 and 178-CL-078]. Both low-fat and high-fat meals decreased the peak and systemic exposures to mirabegron (50 or 100 mg dose) when compared with fasting conditions, however, the magnitude of the food effect was greater for the low-fat than the high-fat meal. Following a low-fat meal, C_{max} was reduced by approximately 64% to 75% and AUC_{inf} was reduced by approximately 47% to 51% relative to the fasted state. Following a high-fat meal, C_{max} was reduced by approximately 39% to 53% and AUC_{inf} was reduced by approximately 17% to 29% relative to the fasted state. No clear difference was observed between male and female subjects.

Refer to the [Investigator's Brochure] for detailed information.

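### Is n = 12 per dose unjustified because the > 80% probability holds only near an observed fed/fasted ratio of 100%?

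*Protocol*

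**What the plan says.** Protocol 9.1 sets the size: "A total of 24 subjects (12 subjects per dose group) will be enrolled". The intrasubject CVs of AUCinf, AUClast and Cmax come from an earlier Chinese phase 1 study at 50 mg and "are estimated to be between 33% and 60"%. The justification takes the top of that range ("Assuming the underlying variability is similar to 60"%) and adds the condition and the conclusion together: "an observed ratio between fasted and fed conditions of 100%, the 90% CI will lie within (60, 167) with > 80% probability". The synopsis (Protocol 1.1) and SAP 3 repeat the statement.

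Protocol 9.6.3 and SAP 6.5.3 analyse each dose separately and report geometric least squares mean ratios with 90% CIs. Neither sets a hypothesis test, an equivalence criterion or a decision rule for the food effect.

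Protocol 2.1.1 gives the background from studies in the US and Japan: "Following a low-fat meal, C_{max} was reduced by approximately 64% to 75% and AUC_{inf} was reduced by approximately 47% to 51"%. The sample-size section does not refer to these results.

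**The concern.** Two features look wrong.

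- **The statement conditions on the estimate.** A sample-size argument normally fixes a true ratio and lets the estimate vary. Fixing the observed ratio at 100% removes the sampling error of the ratio and leaves only the uncertainty in the estimated variance. The probability then comes out much higher than for a true ratio of 100%.
- **The statement is centred on no food effect.** The reductions in Protocol 2.1.1 correspond to fed/fasted ratios of 0.25 to 0.36 for Cmax and 0.49 to 0.53 for AUCinf. A 90% CI contains its point estimate, so at an observed ratio in those ranges it cannot lie inside (60, 167).

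If the sentence were a promise that the study's intervals will fall inside (60, 167), the study would almost certainly break it while performing as designed. The only quantitative support for 12 subjects per dose would then have no bearing on the effect the trial is meant to measure.

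**Working it through.** **Inputs.** From Protocol 9.1: 12 subjects per dose, CV 60%, limits 0.60 and 1.67, two-sided 90% CI. From Protocol 9.6.3: each dose analysed alone. A two-period, two-sequence crossover with 12 completers leaves 12 − 2 = 10 residual degrees of freedom.

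**Step 1: typical interval.**
- Log-scale within-subject SD = √ln(1 + 0.60²) = 0.5545.
- SE of the log ratio = 0.5545 × √(2/12) = 0.2264.
- t(0.95, 10) = 1.8125, so the half-width at the assumed SD is 1.8125 × 0.2264 = 0.410.
- At an observed ratio of 100% the interval is exp(±0.410), or 66.3% to 150.7%.

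**Step 2: the plan's own figure.** With the estimate at 100%, the interval lies within (60, 167) when its half-width is below ln(1/0.60) = 0.5108. The estimated variance follows a scaled chi-square with 10 df, so

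P = P(χ²₁₀ ≤ 10 × (0.5108/0.4103)²) = P(χ²₁₀ ≤ 15.5) = 88.5%.

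The stated > 80% is correct. It stays above 80% for observed ratios of about 96.6% to 103.6%, so the condition need not hold exactly.

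**Step 3: the probability at a true ratio.** Now the estimate also varies, normally around the log of the true ratio with SE 0.2264, independently of the variance. Integrating P(lower limit > 0.60 and upper limit < 1.67) over both gives:

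| True fed/fasted ratio | CV 60% | CV 33% |
|---|---|---|
| 1.00 | 37% | 95% |
| 0.53 | 1.5% | 0.6% |
| 0.49 | 0.6% | 0.1% |
| 0.36 | 0.01% | about 0 |
| 0.25 | about 0 | about 0 |

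A simulation of 2,000,000 trials at CV 60% agrees (37.4% at a true ratio of 1.00; 1.5% at 0.53).

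**Step 4: what the sentence says about precision.** The limits are reciprocal, since 1/0.60 = 1.67. The half-width in Step 2 depends on the SD, n and degrees of freedom, and not on the ratio. The same 88.5% is therefore the probability that the 90% CI lies within 0.60 to 1.67 times the observed ratio, wherever that ratio falls. The simulation gives 88.5% for this event at true ratios of 1.00, 0.53, 0.49, 0.36 and 0.25 alike. Multiplying each earlier ratio by 0.663 and 1.507 from Step 1 gives typical intervals at CV 60%:

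| Parameter | Observed ratio | Typical 90% CI |
|---|---|---|
| Cmax | 25% | 17% to 38% |
| Cmax | 36% | 24% to 54% |
| AUCinf | 49% | 33% to 74% (32.5 to 73.9) |
| AUCinf | 53% | 35% to 80% |

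Each of these excludes 100%. A food effect of the size seen before would be visible with 12 subjects per dose even at the highest CV in the protocol's range.

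**The case for a change.** The best case for a change is that this is the only quantitative justification for the sample size, and a reader who does not work on the log scale may take it as assured performance. Such a reader would see intervals outside (60, 167) and think the plan had failed. The sentence does not say that the width is relative to the ratio, does not mention the earlier low-fat results, and applies a 50 mg CV to 25 mg without saying that this is an assumption. The margin is also limited: the conditional probability is 81% with 11 completers and 72% with 10, and replacement is at the sponsor's discretion.

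Some of this stands. The illustration is centred on a ratio that the earlier studies make unlikely, and a statement of relative precision would be clearer.

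The rest does not carry it to a change. The sentence says openly that the ratio is an observed one, and it claims nothing about a true ratio. The 37% and the 1.5% measure success against a criterion that this estimation study does not have. The 37% also belongs to the top of the CV range; at CV 33% it is 95%. The earlier ratios are results from US and Japanese studies at 50 or 100 mg, and the protocol does not adopt them as planning values. The 50 mg source of the CV is disclosed. Falling to 72% requires the loss of two of 12 subjects in one dose group without replacement, and Protocol 6.3.2.2 provides for replacement into the same sequence.

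**Conclusion.** The concern does not call for a change. The figure is right under its stated condition (88.5% against a claim of more than 80%), and because the log-scale width is free of the ratio, the same figure describes the precision at any food effect. A clearer sentence would carry the same factors, the same probability of about 88% and the same 12 subjects per dose. It would leave the model, the intervals and their interpretation untouched, so nothing is gained beyond readability.

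This rests on log-normal data, 12 completers per dose with 10 degrees of freedom, and an intrasubject CV no worse than about 60% at both doses; the conditional probability reaches 80% at a CV of about 65%. It also rests on the study remaining one of estimation. If (60, 167) were used as an acceptance range, the 37% at a true ratio of 100% and CV 60% would become the relevant figure, and about 22 subjects per dose would be needed to reach 80%. Neither document proposes that use.

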9.2 Analysis Sets

For each sequence, the number and percentage of subjects will be characterized for all randomized subjects and by each analysis set.

9.2.1 Safety Analysis Set

The safety analysis set (SAF) consists of all subjects who receive at least 1 dose of IP.

The SAF will be used for all summaries and analyses of the safety data.

9.2.2 Pharmacokinetic Analysis Set

The pharmacokinetic analysis set (PKAS) consists of all subjects who receive at least 1 dose of IP for which concentration data are available to facilitate derivation of at least 1 primary pharmacokinetic parameter. Inclusion of subjects in the PKAS with missing data or major protocol deviations will be considered by the pharmacokineticist on a case-by-case basis.

The PKAS will be used for all summaries and analyses of the pharmacokinetic data.

9.3 Demographics and Baseline Characteristics

9.3.1 Demographics

Demographics and baseline characteristics (age, sex, race, body weight, height and BMI) will be summarized by dose group, sequence and overall for all randomized subjects.

9.3.2 Subject Disposition

The number and percentage of subjects who completed and discontinued dosing and reasons for dosing discontinuation will be presented for all randomized subjects and for subjects in the SAF by dose group, sequence and overall. Similar tables for investigational period disposition and follow-up disposition will also be presented for all randomized subjects by dose group, sequence and overall. All disposition details and dates of first and last evaluations for each subject will be listed.

9.3.3 Previous and Concomitant Treatment (Medication and Nonmedication Therapy)

Previous and concomitant treatment (medication and nonmedication therapy) will be listed.

9.3.4 Medical History

Medical history for each subject will be listed.

9.3.5 Investigational Product Exposure

The number and percentage of subjects exposed to IP will be summarized by dose group and sequence under fed and fasted conditions.

IP exposure data will be listed.

9.4 Analysis of Efficacy

Not applicable.

9.5 Analysis of Safety

9.5.1 Adverse Events

AEs will be coded using MedDRA. An AE with onset at any time from first dosing until last scheduled procedure will be classified as a TEAE for inclusion in the summary tabulations. An IP-related TEAE is defined as any TEAE with a causal relationship assessed as “yes” by the investigator, or records where the relationship is missing.

An overview and separate summaries of the number and percentage of subjects with TEAEs, drug-related TEAEs, TEAEs leading to withdrawal of dosing, IP-related TEAEs leading to withdrawal of dosing and TEAEs excluding SAEs that equal or exceed a threshold of 5% in any dose group under fed and fasted conditions will be presented by SOC, preferred term, by fed and fasted conditions for each dose group. Also included in the overview are the number and percentage of subjects with serious TEAEs, IP-related serious TEAEs, TEAEs leading to death and IP-related TEAEs leading to death.

AE data will be listed.

9.5.2 Laboratory Assessments

For quantitative clinical laboratory measurements (hematology and biochemistry), descriptive statistics will be used to summarize results and change from baseline by fed and fasted conditions and visit for each dose group.

Laboratory data will be listed.

9.5.3 Vital Signs

Descriptive statistics will be used to summarize vital sign results and changes from baseline for subjects by fed and fasted conditions and time point for each dose group.

Vital signs data will be listed.

9.5.4 Electrocardiogram

9.5.4.1 Routine 12-lead Electrocardiogram

Routine 12-lead ECG data and interpretations will be listed.

9.6 Analysis of Pharmacokinetics

Descriptive statistics will include n, mean, SD, CV, geometric mean, geometric CV, median, minimum and maximum. For the pharmacokinetic parameters t_{max} and t_{lag} , only n, median, minimum and maximum will be calculated.

9.6.1 Plasma Concentrations

Plasma concentrations under both fasted and fed conditions will be listed and summarized using descriptive statistics by scheduled time point for each dose group. Standard graphics including mean plasma concentration-time profiles, overlay (spaghetti) plots and individual subject plasma concentration-time profiles will be produced.

9.6.2 Estimation of Pharmacokinetic Parameters

Noncompartmental analysis will be used for the calculation of plasma pharmacokinetic parameters using Phoenix® (Certara LP, [name]).

Plasma pharmacokinetic parameters under both fasted and fed conditions will be listed and summarized using descriptive statistics for each dose group.

9.6.3 Statistical Analysis of Pharmacokinetic Parameters

To assess the effect of food on the pharmacokinetic of mirabegron, a mixed effects analysis of variance (ANOVA) model with fixed effects for food condition (fed or fasted) and period and subject as a random effect will be fitted on natural logarithm-transformed AUC_{inf} , AUC_{last} and C_{max} . Within the ANOVA, the least squares (LS) mean differences between fed and fasted, along with 90% CIs for the differences will be estimated for 25 and 50 mg mirabegron doses separately.

The LS means for AUC_{inf} , AUC_{last} and C_{max} will be back-transformed to produce the geometric LS means and presented with the number of subjects for each food condition. The geometric LS mean ratios and their corresponding 90% CIs for each pharmacokinetic parameter will be presented by back-transforming and expressed as percentages. The analysis will be repeated if all subjects did not complete both periods using an ANOVA with fixed effects for period, food condition and subject; this analysis will only include subjects with complete data in both periods.

9.7 Analysis of Pharmacodynamics | Immunogenicity

Not applicable.

9.8 Other Analyses

Not applicable.

9.9 Major Protocol Deviations

Major protocol deviations as defined in [Section [10.3](#) Major Protocol Deviations] will be listed.

9.10 Interim Analysis (and Early Discontinuation of the Study)

Not applicable.

9.11 Additional Conventions

As a general principle, no imputation of missing data will be done. Exceptions are the start and stop dates of AEs and concomitant medications if they are missing on day of first IP administration. The imputed dates will be used to assess if the AEs or concomitant medications are treatment emergent or concomitant, respectively. Listings of the AEs and concomitant medications will present the actual partial dates; imputed dates will not be shown.

10 OPERATIONAL CONSIDERATIONS

10.1 Data Collection

The investigator or site designee will enter data collected using an electronic data capture system. In the interest of collecting data in the most efficient manner, the investigator or designee should record data (including clinical laboratory values, if applicable) in the eCRF within 10 working days after the subject's visit. The data will be entered after HGRAC data filing approval if required by site.

The investigator or site designee is responsible to ensure that all data in the eCRFs and queries are accurate and complete and that all entries are verifiable with the source. These documents should be appropriately maintained by the study site.

The monitor should verify the data in the eCRFs with the source and confirm that there are no inconsistencies among them.

Clinical laboratory tests and ECG are performed at a local laboratory.

10.2 Demographics and Baseline Characteristics

10.2.1 Demographics

Demographics and baseline characteristics will be collected as indicated in the Schedules of Assessments [Table 1]. This will include age, sex, race, body weight, height and BMI.

10.2.2 Medical History

A complete medical history will be collected as indicated in the Schedules of Assessments [Table 1].

10.3 Major Protocol Deviations

A protocol deviation is generally an unplanned excursion from the protocol that is not implemented or intended as a systematic change. All deviations from the protocol are to be recorded. A protocol waiver is a documented prospective approval of a request from an investigator to deviate from the protocol. Protocol waivers are strictly prohibited.

The investigator is responsible for ensuring the study is conducted in accordance with the procedures and evaluations described in this protocol and must protect the rights, safety and well-being of subjects. The investigator should not implement any deviation from, or changes of, the protocol, unless it is necessary to eliminate an immediate hazard to subjects.

A major protocol deviation is one that may potentially impact the completeness, accuracy or reliability of data contributing to the primary endpoint or affect the rights, safety or well-being of a subject. Major protocol deviations will have additional reporting requirements.

When a major deviation from the protocol is identified for an individual subject, the investigator or designee must ensure the sponsor is notified. The sponsor will follow up with the investigator, as applicable, to assess the deviation and the possible impact to the safety and/or pharmacokinetic parameters of the subject to determine subject continuation in the study.

The major protocol deviation criteria that will be summarized at the end of the study are as follows:

PD1 - Entered into the study even though the subject did not satisfy entry criteria

PD2 - Developed withdrawal criteria during the study and was not withdrawn

PD3 - Received incorrect dose

PD4 - Received excluded concomitant treatment

The investigator will also assure that deviations meeting IRB/IEC and appropriate regulatory authorities' criteria are documented and communicated appropriately. All documentation and communications to the IRB/IEC and appropriate regulatory authorities will be provided to the sponsor and maintained within the trial master file.

10.4 Study organization

10.4.1 Independent Data Monitoring Committee | Data and Safety Monitoring Board | Monitoring Committee | Adjudication Committee | Other Evaluation Committee(s)

Not applicable.

